1. Patients will come to the Emergency Department or the POC after a supracondylar fracture or periprosthetic distal femur fracture. 2. If they fit all the inclusion and none of the exclusion criteria they will be told about the study either before their surgery if they are lucid, not in pain and can understand the study, or after their surgery when they are lucid, not in pain and can understand the study. If they are not lucid, are in pain, or cannot understand the study during this time they will not be offered participation in the study. 3. They will be told about the study with the understanding that assignment to either partial weight bearing or full weight bearing is standard of care and that physical therapy will conduct the therapy based on their group assignment 4. All questions will be answered and the subject will be given the opportunity to consent 5. They will have a metabolic bone work up done if they are 65 years of age or older which is standard of care. 6. Radiographs will be taken at 6 weeks, 3, 6 and 12 months to determine radiographic healing and/or complications with hardware which is standard of care. 7. Two independent surgeons will review radiographs to determine bridging of 3 or 4 cortices 8. We will measure time to ambulation at 2 weeks, 6 weeks and 3 months. Other variables measured include: Age, gender, date of surgery, Surgeon, Rt/Left, plate (LISS or Locking), smoking status, co-morbidities, perambulatory status, PT participation, time to discharge, discharge disposition, return to baseline ambulation, time to union, pain, Knee society score, knee flexion, radiographic evidence of healing, non-union, malunion, infection, DVT, PE, implant failure/reoperation, Vit D level, death. 9. Patients will complete a health progress report at 2 weeks, 3, 6, and 12 months post-surgery which is standard of care.

Please describe the investigational procedures that will be performed throughout the duration of the study.

Reviewing who heals faster with better outcomes based on assignment to full or partial weightbearing, both of which are standard of care, but for the study, the subject is assigned to one or the other.

Please describe the standard of care procedures that will be performed throughout the duration of the study.

Surgery and anything associated with it.

Will you be assigning or randomizing participants to groups or conditions (e.g., control, placebo)?

Yes

Describe the group assignment.

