We will be looking at two groups: those with periprosthetic distal femur fracture and those with a distal femur fracture proximal to the native knee. Both will have had their distal femur fracture repaired per standard of care. Patients in both groups will then be randomized into two groups: those allowed to bear weight immediately post operatively and those with protected weight bearing post operatively.

Does the research involve surveys/interviews/questionnaires? If so, attach a copy of the interview/survey questions on the Notes & Attachments page.

No

Describe what is known about this topic and why this study is needed. Please include at least two reference citations to support your rationale.

This study is designed to examine if immediate weight bearing on a distal femur fracture fixed with a primary locking plate, either a distal condylar locking plate or a LISS (less invasive stabilization system), is safe and promotes more rapid fracture healing. Historically and currently patients are kept partial weight bearing after fixation of these fractures for 6-12 weeks until callous formation is observed on radiographs. Our hypothesis is that patients that are allowed to bear weight immediately will heal at least as quickly as those that have their weight bearing status protected with the added benefits from early mobilization. Fracture healing will be monitored closely by follow up appointments and complications will be documented. See Lit Review under Notes and Attachments for Scientific Rationale and references.

What method are you going to use to analyze the data?

Descriptive statistics will be performed on the following variables in both groups: Age, gender, date of surgery, Surgeon, Rt/Left, plate (LISS or Locking), smoking status, co-morbidities, perambulatory status, PT participation, time to discharge, discharge disposition, return to baseline ambulation, time to union, pain, Knee society

score, knee flexion, radiographic evidence of healing, non-union, malunion, infection, DVT, PE, implant failure/reoperation, Vit D level, death.

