### Subjects

Indicate the maximum number of subjects to be enrolled or medical records to be reviewed at all sites by the WVU or VAMC research team.

150

Provide a rationale for choosing your sample size.

75 in each group provides 80% power to detect a difference between the groups.

State the requirement(s) to become a participant in the study (e.g., age range, sex, language spoken, class enrollment/ranking).

All patients aged > 18 yo with a distal supracondylar femur fracture will be included, both male and female; Supracondylar distal femur fractures treated with a locked plate, either a distal condylar locking plate or a LISS (less invasive stabilization system), including peri-prosthetic fractures. CPT code 27511

Explain why selection of participants will be equitable addressing gender, ethnicity, and/or race of subjects.

Patients with an intracondylar split, polytrauma patients with associated trauma that will inhibit their ability to weight bear, metastatic disease, incomplete follow up, those with questionable ability to bear weight (ie advanced dementia), open fractures with bone loss, will not be included. Those who are in pain, not lucid, or unable to understand the study at time of consent will not be included.

In outline format and chronological order, describe what will be done to identify and recruit participants (e.g., A, B, C or 1, 2, 3).

1. Patients will come to the Emergency Department or the POC after a supracondylar fracture or periprosthetic distal femur fracture. 2. If they fit all the inclusion and none of the exclusion criteria they will be told about the study either before their surgery if they are lucid, not in pain and can understand the study, or after their surgery when they are lucid, not in pain and can understand the study. If they are not lucid, are in pain, or cannot understand the study during this time they will not be offered participation in the study.

Will any of the subjects be less than 18 years old?

No

Will your study target populations such as pregnant women, fetuses, neonates, or any groups likely to be vulnerable to coercion or undue influence such as children, prisoners, individuals with impaired decision-making capability or economically or educationally disadvantaged persons?

No

Does this research involve participants who could be coerced or unduly influenced, such as current students/employees of research team members?

No

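### The plan only describes its variables; the arm comparison it intends should be prespecified as adjusted for fracture type and a short list of baseline factors

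*Combined protocol and SAP*

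**What the plan says.** The Design section's list of procedures sets out what is collected: "Other variables measured include: Age, gender, date of surgery, Surgeon, Rt/Left, plate (LISS or Locking), smoking status", followed by co-morbidities, walking status, physical-therapy participation, healing outcomes and complications.

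The analysis answer in the same section is one sentence: "Descriptive statistics will be performed on the following variables in both groups", after which the same list is repeated. The run "smoking status, co-morbidities, perambulatory status, PT participation" shows how it is built: three items that read as baseline factors stand beside one that arises after assignment. Outcomes such as time to union, non-union and death follow in the same list. No primary outcome, test, model, interval or adjustment is given.

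On allocation, the Design section first separates periprosthetic from native-knee fractures and then says "Patients in both groups will then be randomized into two groups: those allowed to bear weight immediately post operatively", the alternative being protected weight bearing. I read this as randomisation within fracture type.

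The Subjects section caps enrolment at 150 and justifies it with "75 in each group provides 80% power to detect a difference between the groups".

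**The concern.** The hypothesis and the power statement both need the arms to be compared, but the only stated method is a table of unadjusted summaries. The baseline factors in that table are plausible predictors of healing and walking. The population is broad: adults of any age, with native-knee and periprosthetic fractures together. The protocol itself treats age as relevant to bone, since it calls for a metabolic bone work-up from 65 years.

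Two things are at stake. First, with at most 75 per arm, a comparison that ignores prognostic factors may have less power than one that uses them, and is more exposed to a chance imbalance. Second, whoever later writes the comparison will have to choose covariates from a long, unsorted list. If that happens after the data are seen, the choice can follow the result. It could also take in physical-therapy participation, which assignment may affect.

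**Working it through.** **1. The plan's own figure.** The 75 per group cannot be reproduced: the documents give no endpoint, effect size, variability, alpha or sidedness. Back-solving with 1:1 allocation, two-sided alpha 0.05 and no dropout (all assumed):

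- Continuous outcome: d = (1.96 + 0.8416) × √(2/75) = 2.8016 × 0.1633 = 0.457 SD.
- Time to event, if all 150 patients have the event: HR = exp(2.8016 / √(150 × 0.25)) = exp(0.4575) = 1.58.

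Many inputs fit, so the figure is neither confirmed nor refuted. I take 80% as the starting power.

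**2. Gain from adjustment, continuous outcome.** Let R² be the share of outcome variance explained by k baseline covariates. The residual variance falls by the factor (1 − R²). Estimating k coefficients inflates the variance of the arm effect by about 1 + k/(N − k − 3). With N = 150 and k = 3 (fracture type, age, smoking), that is 1 + 3/144 = 1.0208.

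Power = Φ(2.8016 / √((1 − R²) × inflation) − 1.96)

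| Assumed R² | Power, no penalty | Power, penalty for 3 covariates |
|---|---|---|
| 0 | 80.0% | 79.2% |
| 0.02 | 80.8% | 80.0% |
| 0.05 | 82.0% | 81.2% |
| 0.10 | 84.0% | 83.2% |
| 0.20 | 87.9% | 87.3% |

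Worked case, R² = 0.20: √(0.80 × 1.0208) = 0.9037; 2.8016 / 0.9037 = 3.100; 3.100 − 1.96 = 1.140; Φ(1.140) = 0.873.

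**3. Break-even.** Adjustment pays when 1 − R² is below 1/inflation, which simplifies to R² > k/(N − 3) = k/147. For k = 3 this is 2.0%, for k = 4 (adding baseline ambulation) 2.7%, for k = 5 3.4% and for k = 10 6.8%. This is why the list should be short.

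**4. Time-to-event and binary outcomes.** The table does not carry over to these. In Cox and logistic models there is no residual variance for a covariate to remove. The conditional log ratio moves away from zero, while its standard error stays the same or grows. A simulation with 75 per arm and one standard-normal prognostic covariate (strengths assumed) shows the pattern:

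- Logistic, covariate log OR 0.5: mean standard error of the arm effect 0.348 unadjusted, 0.362 adjusted; power 76% and 78%.
- Cox, covariate log HR 0.5: standard error 0.176 and 0.178.

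So power can rise while the interval does not narrow.

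**5. Rare events.** At an assumed 5% rate, 150 × 0.05 = 7.5 events. That cannot support a model with arm and three or four covariates.

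**The case against.** The strongest objection is that no arm comparison is planned, so none can lose precision; the main gap is the missing primary outcome, test or model and margin. That stands, and it sets the order: adjustment goes with naming the comparison and does not replace it. The point survives because the covariates have to be settled at the same moment, before outcomes are seen.

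Second, an unadjusted comparison in a randomised trial is valid, and the documents give no prognostic strength for any covariate. Both are true. A reader might infer that the planned analysis is biased, or that a known amount of power is being lost. The documents support neither, because the gain depends wholly on an assumed R².

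Third, a reader might infer that adjustment is free and always narrows the interval. It is not free: at R² = 0 power falls from 80.0% to 79.2%, and missing covariate values need a rule. Nor does the narrower interval hold in general for hazard and odds ratios, which are the natural measures for time to union and non-union.

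Fourth, fitting one model to every listed outcome would overreach: some events may be rare, and time to discharge and time to ambulation suit neither linear nor logistic regression. That also stands, and the fix is limited accordingly.

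Finally, *perambulatory status* is not defined. Reading it as pre-injury walking status is an assumption. It is supported by return to baseline ambulation being a listed outcome, which requires the baseline to be known.

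**Conclusion.** The point holds as a modest improvement. The plan intends to compare arms, randomises within fracture type (on the reading above) and already collects likely prognostic factors, but states only unadjusted description. Prespecified adjustment would take power from 80% to about 81–87% for a continuous outcome. This assumes R² of 5–20%, three covariates, two-sided alpha 0.05, 1:1 allocation and full follow-up of 150. There is no gain below an R² of about 2%. For time to union and binary outcomes the expected benefit is power and protection against chance imbalance, and its size cannot be fixed from the documents. The lack of a named primary outcome and comparison remains the larger issue.

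**What to change.** Together with naming a primary outcome and an inferential comparison of the arms, state before outcome data are examined:

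- **Model.** Arm, fracture type, age (continuous) and smoking (yes/no), for the main comparison and other sufficiently frequent outcomes. Time to union is the natural main outcome given the healing hypothesis, but the plan does not name it. Add baseline ambulatory status for ambulation outcomes, once that variable is defined.
- **Form.** Linear regression for continuous outcomes and logistic for binary ones. Use a time-to-event model for time to union, discharge and ambulation. For union, the method must allow for healing being seen only at the radiographs at 6 weeks and 3, 6 and 12 months.
- **Leading estimate.** The adjusted one, with its 95% interval and the unadjusted estimate beside it.
- **Limits.** Leave rare events such as DVT, PE and death unadjusted. Do not adjust for physical-therapy participation or any other post-assignment variable. Leave surgeon out, since the number of surgeons is not given.
- **Missing covariates.** One stated rule.

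The cost is a little more analysis work and no new data. The downsides are a few degrees of freedom and a conditional estimand for hazard and odds ratios, which is why the unadjusted result is shown too.

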### Expedited Review

Is this study only minimal risk?

Yes

Does the research qualify for Expedited Review Category 1 - clinical studies of FDA-approved drugs or medical devices? (See More Information)

No

Does the research qualify for Expedited Review Category 2 - blood sample collection? (See More Information)

No

Does the research qualify for Expedited Review Category 3 - noninvasive collection of biological specimens? (See More Information)

No

Does the research qualify for Expedited Review Category 4 - noninvasive standard of care procedures? (See More Information)

No

Does the research qualify for Expedited Review Category 5 - evaluation of data (e.g., medical records review)? (See More Information)

Yes

Does the research qualify for Expedited Review Category 6 - voice, video, digital, or image recordings? (See More Information)

No

Does the research qualify for Expedited Review Category 7 - behavior, surveys, interviews, etc.? (See More Information)

No

Briefly describe how the research meets the requirements of the expedited category(ies) selected.

Full or partial weight bearing after a supracondylar distal femur fracture is standard of care. Review of medical records to determine the variables we want to collect: standard of care patient reported outcomes at regular follow up visits.

Does the study involve intervention and/or manipulation of the subjects or the subjects' environment (e.g., educational intervention or training, experimental or quasi-experimental design)?

No

Is the research categorized as interventional medical research?

No

Will subjects intentionally be deceived as to the purpose of the study?

No

### HIPAA

Does the research involve protected health information (PHI) or personally identifiable information (PII)?

Yes

Will the HIPAA and consent forms be combined? If not, attach a separate HIPAA Authorization Form to the Notes & Attachments page.

Yes

Are you requesting a HIPAA waiver? If yes, attach a HIPAA Waiver Form on the Notes & Attachments page.

No

Will you be transferring or receiving identifiable data or samples in collaboration with another institution? If yes, attach a signed HIPAA data use/data sharing agreement or Material Transfer Agreement (MTA) or a Biological Material Transfer Agreement to the Notes & Attachments page.

No

Will the research conducted at a covered entity involve only de-identified data? If yes, attach a HIPAA De-Identification Certification Form on the Notes & Attachments page.

No

Will the study involve only non-living individuals? If yes, attach a HIPAA Decedents Form on the Notes & Attachments page.

No

### Subjects

Indicate the maximum number of subjects to be enrolled or medical records to be reviewed at all sites by the WVU or VAMC research team.

150

Provide a rationale for choosing your sample size.

75 in each group provides 80% power to detect a difference between the groups.

State the requirement(s) to become a participant in the study (e.g., age range, sex, language spoken, class enrollment/ranking).

All patients aged > 18 yo with a distal supracondylar femur fracture will be included, both male and female; Supracondylar distal femur fractures treated with a locked plate, either a distal condylar locking plate or a LISS (less invasive stabilization system), including peri-prosthetic fractures. CPT code 27511

Explain why selection of participants will be equitable addressing gender, ethnicity, and/or race of subjects.

Patients with an intracondylar split, polytrauma patients with associated trauma that will inhibit their ability to weight bear, metastatic disease, incomplete follow up, those with questionable ability to bear weight (ie advanced dementia), open fractures with bone loss, will not be included. Those who are in pain, not lucid, or unable to understand the study at time of consent will not be included.

In outline format and chronological order, describe what will be done to identify and recruit participants (e.g., A, B, C or 1, 2, 3).

1. Patients will come to the Emergency Department or the POC after a supracondylar fracture or periprosthetic distal femur fracture. 2. If they fit all the inclusion and none of the exclusion criteria they will be told about the study either before their surgery if they are lucid, not in pain and can understand the study, or after their surgery when they are lucid, not in pain and can understand the study. If they are not lucid, are in pain, or cannot understand the study during this time they will not be offered participation in the study.

Will any of the subjects be less than 18 years old?

No

Will your study target populations such as pregnant women, fetuses, neonates, or any groups likely to be vulnerable to coercion or undue influence such as children, prisoners, individuals with impaired decision-making capability or economically or educationally disadvantaged persons?

No

Does this research involve participants who could be coerced or unduly influenced, such as current students/employees of research team members?

No

Does the protocol deal with cancer prevention, treatment, or diagnosis (including surveys)?

No

Has this protocol been reviewed by Clinical Trials Working Group (CTWG)? If yes, please attach the CTWG's correspondence on the Notes & Attachments page.

No

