**Design**

Please provide a lay summary (written at 6th grade level) that includes a statement about the purpose and the general aims of the research.

This study is designed to examine if immediate weight bearing on a distal femur fracture fixed with a primary locking plate, either a distal condylar locking plate or a LISS (less invasive stabilization system), is safe and promotes more rapid fracture healing. Historically and currently patients are kept partial weight bearing after fixation of these fractures for 6-12 weeks until callous formation is observed on radiographs. Our hypothesis is that patients that are allowed to bear weight immediately will heal at least as quickly as those that have their weight bearing status protected with the added benefits from early mobilization. Fracture healing will be monitored closely by follow up appointments and complications will be documented.

Fully describe all procedures to be performed, from start to finish, numbering your procedures 1,2,3 or A, B, C (e.g., 1. Recruiting, 2. Consent, 3. Collecting data, 4. How findings will be shared, etc.).

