### **Potential Benefits**

Is there any known benefit to the individual subject as a result of participating in the research? Payments to subjects should not be included in this section, but addressed in the Payments/Reimbursements section.

If our hypothesis is correct, those subjects who do full weight bearing will heal faster and suffer less complications.

Describe the potential benefit(s) to society and/or scientific / medical knowledge of the planned work.

Understanding and sharing information gathered from the research study re: benefit or no benefit to full weight bearing after a supracondylar distal femur fracture.

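### The stated 80% power belongs to no planned test or interval, the objective is not fixed as superiority or non-inferiority, and no loss allowance is stated within the 150 maximum

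*Combined protocol and SAP*

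**What the plan says.** All references are to the combined protocol and SAP.

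- **Size.** The Subjects section answers the prompt "Indicate the maximum number of subjects to be enrolled" with 150. The rationale is one sentence: "75 in each group provides 80% power to detect a difference between the groups".
- **Loss.** The same section lists "metastatic disease, incomplete follow up" among the reasons for not being included. The Design section states: "Radiographs will be taken at 6 weeks, 3, 6 and 12 months". No loss rate or allowance appears.
- **Analysis.** Asked for the analysis method, the Design section answers: "Descriptive statistics will be performed on the following variables in both groups". A list of about 25 variables follows, with none marked as primary. Elsewhere, under investigational procedures, the Design section says that the study will look at who heals faster and with better outcomes according to the assigned weight bearing.
- **Objective.** The Design section asks whether immediate weight bearing "is safe and promotes more rapid fracture healing", and hypothesises that these patients "will heal at least as quickly as those that have their weight bearing status protected". Potential Benefits restates the hypothesis: "those subjects who do full weight bearing will heal faster and suffer less complications".

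**The concern.** A power figure describes a particular analysis: a test or interval, for one outcome, at one alpha, against one effect or margin. Here the figure is given and the analysis is not. If the plan is followed as written, nothing in it rejects a null hypothesis or bounds a difference, so the claimed 80% is a property that the plan does not have.

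The hypothesis raises the stakes. Healing at least as quickly is a non-inferiority claim, which needs an interval set against a margin. Two sets of descriptive summaries do not provide that, and neither would a finding of no significant difference. The trial could finish without being able to support or refute its own hypothesis, and a reader could not tell what a null result rules out.

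The loss question adds to this. With enrolment capped at exactly twice 75, there is no visible room for patients whose outcome is never observed. Whether follow-up will be complete also cannot be known at enrolment, so listing incomplete follow-up beside the screening exclusions does not deal with it.

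**Working it through.** **1. Can the plan's figure be reproduced?** No. Outcome, effect size, variability or rates, alpha, sidedness and test are all absent. It can only be inverted. Assume two-sided 5% and 80% power, so k = 1.960 + 0.842 = 2.802. The detectable standardised difference is k x sqrt(2/n). With n = 75 this is 2.802 x sqrt(2/75) = 0.457 SD. So 75 per arm is compatible with 80% power for a difference near 0.46 SD, but nothing in the documents says that this was the basis.

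**2. Is there room for loss?** 2 x 75 = 150, the stated maximum. If 75 is the evaluable number, the room is zero. If 75 already includes an allowance, the text does not say so.

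**3. What would loss cost?** Assume that 75 evaluable per arm gives exactly 80% at two-sided 5%, and that a lost patient contributes no outcome. Then power(n) = Phi(2.802 x sqrt(n/75) - 1.960). The loss rates are assumptions.

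| Loss | Evaluable per arm | Power | Detectable difference at 80% power |
|---|---|---|---|
| 0% | 75 | 80% | 0.457 SD |
| 10% | 67.5 | Phi(0.698) = 75.7% | 0.482 SD |
| 20% | 60 | Phi(0.546) = 70.7% | 0.511 SD |

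These falls are upper limits in two cases. For an early outcome, later loss does not matter: ambulation is measured at 2 weeks, 6 weeks and 3 months, so loss after 3 months would not affect it. For time to union, a patient who unites before being lost still contributes the event.

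**4. What precision could 150 give?** For a difference in the proportion united, the 95% half-width is 1.960 x sqrt(2p(1-p)/n). With p = 0.80, an assumed union rate:
- n = 75 per arm: 1.960 x sqrt(0.32/75) = 0.128, about +/-13 points.
- n = 60 per arm: 1.960 x sqrt(0.32/60) = 0.143, about +/-14 points.

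**5. Objective, side by side.** More rapid healing (Design) and faster healing with fewer complications (Potential Benefits) are superiority statements, and they fit power to detect a difference (Subjects). Healing at least as quickly (Design) is a non-inferiority statement. No margin is given anywhere, so the power sentence cannot be attached to the non-inferiority reading.

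**The case against.** Several objections have force.

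- **An intent to compare is stated.** This stands. The Design section does say that healing will be reviewed by weight-bearing assignment. It would be wrong to infer that no comparison is meant. What is missing is any inferential method for making it.
- **Loss need not reduce power.** This stands in part. The effect depends on the outcome and when it is measured, and the outcome is unnamed. A reader might infer that any loss takes power below 80%. The documents support that only if 75 is the evaluable number and the powered outcome needs follow-up that some patients do not complete.
- **Group could mean fracture type.** The Design section first uses the word for periprosthetic and native-knee fractures, so a reader might infer 75 per fracture type and far fewer per arm within each type. The documents do not support this. Design and Consent Procedures both use group assignment for the weight-bearing arm, and no quota by fracture type is set. A one-line clarification is enough.
- **The objective wordings are nested.** Healing faster implies healing at least as quickly, so they do not flatly contradict each other. That is fair. But the two claims need different analyses, and the plan picks neither.
- **This is a short review form, and details may be in an attachment.** The form asks for both a sample-size rationale and an analysis method. The literature review attachment, which was not available, is cited for scientific rationale and references. The sample-size answer does not point to it. Missing outcome, effect and alpha alone would be only missing detail; the point rests on a power claim paired with a descriptive-only analysis.

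**Conclusion.** The point holds in this form: the plan claims 80% power but specifies no test or interval that could have it, and does not fix its objective as superiority or non-inferiority. This conclusion needs no assumed number.

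The loss element is conditional. Under the assumptions shown, power is about 76% at 10% loss and 71% at 20%, and the fall is smaller for an early outcome or for time to union. The documents give no loss rate, union rate or alpha, so these figures show scale only.

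A reader might also infer that 75 per group is too few. The documents do not support that. The number is unverifiable, and it is compatible with 80% power for a moderate standardised difference.

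**What to change.** Keep the maximum at 150. A larger trial would be another way to absorb losses, but it costs patients and is not needed to make the statement correct.

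1. **Design, analysis method.** Add: *The primary outcome [one healing outcome and time point] will be compared between the weight-bearing arms as randomised, pooling fracture types, with a 95% confidence interval.*
2. **Design and Potential Benefits.** State one objective in both places: superiority, or non-inferiority with a justified margin. Choose outcome, objective and margin without sight of accrued outcome data, and date the change. The protocol notes run from 2015 to 2019, and the documents do not show whether outcome data already exist.
3. **Subjects, sample size.** Restate the power, or the detectable difference or margin, for that outcome and alpha at the evaluable number expected from 150 randomised. Alternatively, state that 75 already includes a loss allowance and give the evaluable number. If no margin can be justified, state the expected precision, in the form of step 4 of the working, with the assumed union rate declared.
4. **Subjects, wording.** Write *75 per weight-bearing arm*.

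Cost: a little more analysis work, and a stated power that is less favourable or a margin that is wider. No extra patients or visits are needed.
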